9.4.2 Efficacy Analyses

In general, efficacy analyses will be performed using the FAS and the observed data at each visit for the study eye and qualifying non-study eyes for most ocular measures or overall for subject-level measurements. In the case of the biomarker test (MMP-9), analysis will be for the study eye only. Analysis of mean CFB in tCFS and eye [REDACTED] will also be performed using the PP Analysis Set as documented in the SAP.

9.4.2.1 Primary Efficacy Analyses

Primary Estimands: The primary estimands are the treatment differences between SY-201 Ophthalmic Solution arms and vehicle for mean CFB to Day 60 in tCFS using study eyes and mean CFB to Day 60 in [REDACTED] score using the FAS.

Target Population: Subjects with DED who meet the study entry criteria.

Treatment Condition(s): Treatment condition is based on the randomized treatment group.

Population-level Summaries: The difference in the mean CFB to Day 60 in tCFS using study eyes and the difference in mean CFB to Day 60 in [REDACTED] score and their p-values and corresponding 95% confidence intervals.

[figure not shown]
The proposed procedures to handle missing data and intercurrent events are as follows:

- Discontinuation of study therapy with continued participation in the study
 - Treatment Policy – no imputation; use observed data
- Receipt of rescue therapy
 - Treatment Policy – no imputation; use observed data
- Missing data with or without withdrawal, regardless of reason
 - Hypothetical approach – missing data will be accounted for assuming missing at random (MAR) using mixed-model repeated measures (MMRM).

Mean CFB in tCFS will be analyzed using an MMRM model. The model will include the baseline measurement, treatment, time, and treatment by time interaction as fixed effects, with a random effect for site. An unstructured covariance among repeated measurements is assumed. A similar model for the subject-level mean CFB in [REDACTED] score will be used.

Additional sensitivity analyses will be described in the SAP.

9.4.2.2 Secondary Efficacy Analyses

9.4.3 Safety Analyses

Safety analyses will be performed on all subjects in the Safety Analysis Set. The assessment of safety will be based on the summary of ocular and non-ocular AEs, laboratory measurements, BCVA, IOP, ophthalmic exams using slit lamp biomicroscopy and dilated ophthalmoscopy, and drop comfort assessment. Summaries will be provided by treatment group, and for ocular assessments separately by eye.

9.4.3.1 Adverse Events

AEs will be coded using MedDRA (most current version) and categorized by system organ class using preferred terms. Separate summaries of AEs related to treatment (as reported by the Investigator) and by severity will be presented. The number of deaths and SAEs will also be presented, and events leading to discontinuation from the study will be listed and tabulated.

9.4.3.2 Clinical Laboratory Tests

Summary statistics for observed and CFB for serum chemistry and hematology laboratory tests will be presented.

9.4.3.3 Other Safety Evaluations

Summary statistics for observed and CFB for BCVA, IOP, and drop comfort assessment will be presented. Abnormalities in slit lamp biomicroscopy and dilated ophthalmoscopy will be summarized by frequency and percentage.

9.5 Interim Analysis

Not applicable.

9.6 Subgroup Analyses

Subgroup analyses will include testing of the mean CFB in tCFS, [REDACTED] score, and secondary endpoints in subgroups based on MMP-9 level in the [REDACTED] at baseline (Visit 2): subjects with elevated MMP-9 level and [REDACTED] The threshold for elevated MMP-9 will be defined in the SAP.

Additional subgroup analyses will be described in the SAP.

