9.2 Sample Size Determination

For mean change from baseline to Day 60 in tCFS, a sample size of 45 SY-201-treated subjects versus 45 vehicle-treated subjects will have 87.9% power to detect an effect size of 2.0 units with a standard deviation of 3.0 for an unpaired t-test with a 2-sided alpha = 0.05.

For mean change from baseline to Day 60 in dry eye symptom [REDACTED], a sample size of 45 SY-201-treated subjects versus 45 vehicle-treated subjects will have 83.5% power to detect an effect size of 1.5 units with a standard deviation of 2.4 for an unpaired t-test with a 2-sided alpha = 0.05.

Fifty (50) subjects per treatment arm, for a total 200 subjects, will be enrolled to allow for some dropout of subjects.

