For analysis of efficacy endpoints, longitudinal models will model the change from baseline of each endpoint as the dependent variable with the baseline measurement of the corresponding endpoint as a covariate and treatment group as the main effect. A random effect for site will be added to account for site-to-site variability.

Subgroups

Subgroup analyses will include testing of the mean CFB in tCFS,

Subgroup analyses by sex and age group (<65 years, ≥65 years) may also be performed.

Multiplicity

To control for type I error, comparisons will be made within each active dose level of SY-201 Ophthalmic Solution compared to Vehicle. In other words, the primary endpoints will be compared sequentially between SY-201 Ophthalmic Solution 2.0% and Vehicle, first testing tCFS and, if statistically significant, . Should both endpoints achieve statistical significance for the 2.0% dose, testing will proceed to Y-201 Ophthalmic Solution 1.0% versus Vehicle, first testing tCFS and, if statistically significant, . Should both endpoints achieve statistical significance for the 1.0% dose, testing will proceed to SY-201 Ophthalmic Solution 0.5% and Vehicle, first testing tCFS and, if statistically significant, . In other words, the first non-significant result in this testing hierarchy of six hypotheses will imply that subsequent tests are non-significant.

Missing Data and Outliers

Every attempt will be made to capture all study data. All analyses will utilize observed data only. Analysis of continuous efficacy endpoints using MMRM assumes missing at random (MAR). Sensitivity analyses of the primary endpoints will be performed utilizing control-based pattern imputation, last observation carried forward (LOCF), and baseline observation carried forward (BOCF).

Visit Windows

The nominal visits listed in the eCRF will be used in the summaries. In general, unscheduled visits will not be summarized in tables unless otherwise noted.

Missing Dates

Missing dates that occur for prior or concomitant medications or adverse events will be queried for a date. If no date is obtained, the following imputation rules will apply:

- For start dates, if the given year (or year-month) is the same as study drug administration, the start date will be imputed as study drug administration date; otherwise, missing month-day (or day) will be imputed as '01-01' (or '01').

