9.7.1.5.1. Primary Efficacy Analysis

Primary Estimands: The primary estimands are the treatment differences between SY-201 Ophthalmic Solution arms and vehicle for mean CFB to Day 60 in tCFS using study eyes and mean CFB to Day 60 in eye [REDACTED] using the FAS.

Target Population: Subjects with DED who meet the study entry criteria.

Endpoints: Change from baseline at Day 60 for tCFS using study eyes and change from baseline at Day 60 for eye dryness score.

Treatment Condition(s): Treatment condition is based on the randomized treatment group.

Population-level Summaries: The difference in the mean CFB to Day 60 in tCFS using study eyes and the difference in mean CFB to Day 60 in eye dryness score and their p-values and corresponding 95% confidence intervals.

The proposed procedures to handle missing data and intercurrent events are as follows:

- Discontinuation of study therapy with continued participation in the study
 - Treatment Policy – no imputation; use observed data
- Receipt of rescue therapy
 - Treatment Policy – no imputation; use observed data
- Missing data with or without withdrawal, regardless of reason
 - Hypothetical approach – missing data will be accounted for assuming missing at random (MAR) using mixed-model repeated measures (MMRM).

Mean CFB in tCFS will be analyzed using a MMRM model. The model will include the baseline measurement, treatment, time, and treatment by time interaction as fixed effects, with a random effect for site. An unstructured covariance among repeated measurements is assumed. A similar model for the subject-level mean CFB in eye dryness score will be used.

Sample repeated measures model code:

```
PROC MIXED DATA=indata;
  CLASS subject center visit treatment(REF='Vehicle');
  MODEL change = baseline_value visit treatment visit*treatment / Solution DDFM=KR;
  REPEAT visit / SUBJECT=subject TYPE=UN;
```

```
RANDOM center;
LSMEANS treatment*visit / slice = visit DIFF CL;
RUN;
```

If the model fails to converge using this covariance structure, spatial power or compound symmetry will be implemented in this order.

Sensitivity analyses of the primary endpoints will be performed utilizing control-based pattern imputation, last observation carried forward (LOCF), and baseline observation carried forward (BOCF).

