9.8.3. SAP Amendments

The SAP was amended to modify the MMP-9 subgroup analyses to be based on baseline tCFS. A Per Protocol Analysis Set will not be defined.

REFERENCES

1. Mozzicato P. (2009). MedDRA: An overview of the medical dictionary for regulatory activities. *Pharmaceutical Medicine* 23: 65-75.
3. SAS Institute Inc. What's New in Base SAS® 9.4 and SAS® Viya®. (2013). SAS Institute Inc., Cary, NC, USA.
4. SAS Institute Inc. (2020). SAS/STAT User's Guide. SAS Institute Inc., Cary, NC, USA.

[figure not shown]

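### Subgroup effects are to be tested inside each subgroup, and no legible text estimates the difference between subgroups, so a uniform effect would look subgroup-specific about half the time per dose

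*Protocol*

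**What the plan says.** Protocol 9.6 opens with "Subgroup analyses will include testing of the mean CFB in tCFS" and, after a redaction, continues "score, and secondary endpoints in subgroups based on MMP-9 level in the". It leaves the cut-point to the SAP: "The threshold for elevated MMP-9 will be defined in the SAP".

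The Subgroups paragraph of SAP 9.7.1 starts with the same words as the protocol and then breaks off. It resumes with an option: "Subgroup analyses by sex and age group (<65 years, ≥65 years) may also be performed". SAP 9.8.3 changes the main subgroup factor: "The SAP was amended to modify the MMP-9 subgroup analyses to be based on baseline tCFS". The SAP synopsis still names MMP-9.

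The general conventions in SAP 9.7.1 set 0.05 with two-sided p-values as the default for any test not otherwise specified. The primary model in SAP 9.7.1.5.1 is given as "The model will include the baseline measurement, treatment, time, and treatment by time interaction as fixed effects, with a random effect for site", and the sample SAS code there matches. It has no subgroup term. The six-step testing hierarchy contains no subgroup test, and no legible text says how subgroup results are to be interpreted.

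**The concern.** A subgroup analysis is meant to answer whether the effect differs between subgroups. Separate p-values inside each subgroup do not answer it. Each compares an effect with zero, and each depends on how many subjects fall in that subgroup. In a comparison sized at 45 per arm, the same true effect can easily be significant in one part and not in the other by chance or because the parts are unequal.

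What is at stake is how supportive results are read after a phase 2 dose-response trial. A result in one subgroup only could be taken as evidence that the drug works only there, when the data say little about any difference.

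**Working it through.** **Inputs.** Protocol 9.2 states that "a sample size of 45 SY-201-treated subjects versus 45 vehicle-treated subjects will have 87.9% power to detect an effect size of 2.0 units". The SD behind that figure is 3.0, and the calculation is for a two-sample t-test at two-sided 0.05. The symptom endpoint has a difference of 1.5 and SD 2.4. The subgroup split is an assumption, because no prevalence or cut-point is legible; splits from 50:50 to 80:20 are shown.

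**Step 1: reproduce the plan's power.** Two-sample t-test, noncentral t, df = 88, noncentrality = 2.0 / (3.0 × √(2/45)) = 3.16. Power is 87.85%, against 87.9% stated. For the symptom endpoint it is 83.45%, against 83.5% stated. Both reproduce.

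**Step 2: the same effect in both subgroups.** At an equal split there are 22.5 per arm in each. Noncentrality = 2.0 / (3.0 × √(2/22.5)) = 2.24, df = 43, power p = 58.9%. The subgroups contain different subjects, so:
- both significant: p² = 34.7%
- exactly one: 2p(1 − p) = 2 × 0.589 × 0.411 = 48.4%
- neither: (1 − p)² = 16.9%
- one named subgroup only: 0.589 × 0.411 = 24%

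For unequal splits, exactly one = p₁(1 − p₂) + p₂(1 − p₁):

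| Split | Per arm | Power, larger / smaller | Exactly one significant | Larger only / smaller only |
|---|---|---|---|---|
| 50:50 | 22.5 / 22.5 | 58.9% / 58.9% | 48% | 24% / 24% |
| 60:40 | 27 / 18 | 67.2% / 49.3% | 50% | 34% / 16% |
| 70:30 | 31.5 / 13.5 | 74.0% / 38.4% | 56% | 46% / 10% |
| 80:20 | 36 / 9 | 79.7% / 26.5% | 64% | 59% / 5% |

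With all 50 per arm, exactly one is significant 46% to 64% of the time over the same splits. For the symptom endpoint at 45 per arm it is 50% to 63%.

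**Step 3: three doses sharing one vehicle arm.** In a simulation (100,000 runs, all doses with the design effect, 45 per arm, splits 50:50 to 70:30), at least one dose showed exactly one significant subgroup in 81% to 85% of runs for tCFS.

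**Step 4: the interaction test on the same data.** At two-sided 0.05 it flagged the uniform effect in about 5% of runs per dose, and in about 12% to 13% for at least one of the three doses.

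**Step 5: precision of the interaction.** At an equal split, SE = 3.0 × √(2/22.5 + 2/22.5) = 1.265, so the 95% CI is ±1.96 × 1.265 = ±2.5 units. By the normal approximation, power to detect a 2.0-unit difference between subgroup effects is 35%, falling to 24% at 80:20. The difference detectable with 80% power at an equal split is (1.96 + 0.84) × 1.265 = 3.5 units.

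**The case against.** The strongest objection is that the paragraph where an interaction test would be stated is the one that cannot be read in full. The Subgroups text in SAP 9.7.1 breaks off, and the secondary-analysis sections are blank. The primary model lacks a subgroup term, but that says little about the model meant for subgroups. This stands: a reader might infer that the plan has no interaction analysis, and the documents do not allow that. They show only that none is legible.

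A reader might also infer that the sponsor will claim a subgroup effect, or choose an enriched population, from the within-subgroup p-values. Neither document says so. They plan the tests and give no legible decision rule.

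Nor is it right that significance in the high subgroup alone is a coin toss. The 48% covers both directions. A named direction has a 24% chance at an equal split, and otherwise depends on which subgroup is larger, which is not known.

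It is also tempting to set the 1 − 0.95² = 9.75% chance of at least one significant subgroup under no effect against the 5% of an interaction test. Those are error rates for different hypotheses, so the comparison is not used here.

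The figures rest on an unadjusted t-test, while the planned MMRM adjusts for baseline. SD 3.0 within each subgroup is untested, particularly when baseline tCFS defines the subgroup. The percentages would move, but two separate p-values would still not estimate a difference.

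Finally, the interaction test has low power. That is true, and it is a reason to report the interval.

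**Conclusion.** The point holds as a matter of interpretation. The legible plan tests the endpoints inside subgroups and nowhere estimates the difference between them. If the design effect were identical in both subgroups, exactly one would be significant about half the time per dose for tCFS: 48% at an equal split and 64% at 80:20. An interaction test would flag such an effect about 5% of the time per dose.

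This rests on the assumed splits, the t-test of the sample-size section, 45 per arm and a common SD of 3.0. It applies whether MMP-9 or baseline tCFS defines the subgroups.

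It does not touch the primary type I error, because no subgroup test is in the hierarchy. The change is worth making because it is cheap, but the primary analysis does not depend on it. The sponsor should first confirm what the redacted SAP text contains.

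**What to change.** If the redacted text does not already do so, amend SAP 9.7.1 (Subgroups) before unmasking:

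- Fit one MMRM to the whole FAS. Keep the baseline covariate and the existing terms, and add subgroup, subgroup-by-visit, treatment-by-subgroup and treatment-by-subgroup-by-visit.
- For each dose, report the Day 60 difference between subgroup effects with its 95% CI as the subgroup result.
- Show within-subgroup estimates with CIs as descriptive.
- Label the analysis exploratory. The SAP's exploratory efficacy analysis section now reads as not applicable, so it needs a matching edit.
- For baseline tCFS or log MMP-9, also fit a continuous treatment-by-baseline term, which does not depend on a cut-point.
- Reconcile the subgroup factor between Protocol 9.6, the SAP synopsis and SAP 9.8.3.

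The cost is a few lines of SAP text and a few model terms, with no new data or subjects. The downside is the low power shown above. The SAP should therefore also state that a non-significant interaction is not evidence of a uniform effect.

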9.7 Exploratory Analyses

Not applicable.

9.8 Missing or Unused Data

Missing data for primary endpoints will be considered MAR with the analysis using MMRM. Otherwise, observed data will be analyzed. All data collected in this study will be presented in individual subject data listings for all subjects at each visit.

9.9 Tabulation of Individual Participant Data

All data collected in this study will be presented in individual subject data listings for all subjects.

10. Supporting Documentation and Operational Considerations

10.1 Regulatory Issues, Ethical Concerns, and Study Oversight

10.1.1 Informed Consent Process

10.1.1.1 Consent Documents

Consent forms describing in detail the study intervention, study procedures, and risks are given to the participant and written documentation of informed consent is required prior to any procedures being done specifically for the study.

10.1.1.2 Consent Procedures and Documentation

Informed consent is a process that is initiated prior to the individual's agreeing to participate in the study and continues throughout the individual's study participation. Consent forms will be Institutional Review Board (IRB) approved and the participant will be asked to read and review the document. The Investigator will explain the research study to the participant and answer any questions that may arise. A verbal explanation will be provided in terms suited to the participant's comprehension of the purposes, procedures, and potential risks of the study and of their rights as research participants. The participant will have the opportunity to carefully review the written consent form and ask questions prior to signing. The participant should have the opportunity to discuss the study with his/her family or surrogates or think about it prior to agreeing to participate. The participant will sign the informed consent document prior to any procedures being done specifically for the study. Participants must be informed that participation is voluntary and that they may withdraw from the study at any time, without prejudice. A copy of the signed and dated informed consent document will be given to the participants for their records. The informed consent process will be conducted and documented in the source document (including the date), and the form signed, before the participant undergoes any study-specific procedures. The rights and welfare of the participants will be protected by emphasizing to them that the quality of their medical care will not be adversely affected if they decline to participate in this study.

10.1.2 Study Discontinuation and Closure

This study may be temporarily suspended or prematurely terminated if there is sufficient reasonable cause. Written notification, documenting the reason for study suspension or termination, will be provided by the suspending or terminating party to study participants, Investigators, funding agency, the Investigational New Drug (IND) or Investigational Device Exemption (IDE) Sponsor, and regulatory authorities as applicable. If the study is prematurely terminated or suspended, the Principal Investigator (PI) will promptly inform study participants, the IRB, and the Sponsor and will provide the reason(s) for the termination or suspension. Study participants will be contacted, as applicable, and be informed of changes to study visit schedule.

Circumstances that may warrant termination or suspension may include, but are not limited to:

- Determination of unexpected, significant, or unacceptable risk to participants
- Demonstration of efficacy that would warrant stopping
- Insufficient compliance to protocol requirements
- Data that are not sufficiently complete and/or evaluable
- Determination that the primary endpoint has been met
- Determination of futility

Study may resume once concerns about safety, protocol compliance, and data quality are addressed, and satisfy the sponsor, IRB, and/or FDA.

10.1.3 Confidentiality and Privacy

Participant confidentiality and privacy will be strictly held in trust by the participating Investigators, their staff, and the Sponsor(s) and their interventions. This confidentiality will be extended to cover testing of laboratory samples in addition to the clinical information relating to participants. Therefore, the study protocol, documentation, data, and all other information generated will be held in strict confidence. No information concerning the study or the data will be released to any unauthorized third party without prior written approval of the Sponsor.

All research activities will be conducted in as private a setting as possible.

The Study Monitor, other authorized representatives of the Sponsor, representatives of the IRB, regulatory agencies, or pharmaceutical company supplying study product will be able to inspect all documents and records required to be maintained by the Investigator, including but not limited to medical records (i.e., office, clinic, or hospital) and pharmacy records for the participants in this study. The clinical study site will permit access to such records.

The study participant's contact information will be securely stored at each clinical site for internal use during the study. At the end of the study, all records will continue to be kept in a secure location for as long a period as dictated by the reviewing IRB, institutional policies, or Sponsor requirements.

Study participant research data, which is for purposes of statistical analysis and scientific reporting, will be transmitted to and stored at Lexitas Pharma Services, Inc. This will not include the participant's contact or identifying information. Rather, individual participants and their research data will be identified by a unique study identification number. The study data entry and study management systems used by clinical sites and by Lexitas Pharma Services, Inc., research staff will be secured and password protected. At the end of the study, all study databases will be de-identified and archived at Lexitas Pharma Services, Inc.

10.1.4 Clinical Monitoring

Lexitas Pharma Services, Inc., will conduct the clinical monitoring for this study. A Clinical Monitoring Plan (CMP) is to be used, which will describe in detail who will conduct the monitoring, at what frequency monitoring will be done, at what level of detail monitoring will be performed, and the distribution of monitoring reports.

